Title of Research Project: Effectiveness of ASTYM treatment when added to traditional therapy for treatment of de Quervain's tenosynovitis

Principal Investigator: [name], MS, OTR/L

Co-Investigators: [name], OTR/L, CHT; [name], OTR/L, CHT, [name], OTR/L, CHT; [name], MS, MPH, OTR/L; [name], OTR/L, [name], OTR/L, CHT

IRB# s14-01059
NCT# NCT02442622

Table of Contents

I.	Purpose of Study and Background	2-7
1)	Purpose of Study	2
2)	Background	2-5
3)	Study Design	6
II.	Characteristics of Research Population	7
1)	Number of Subjects	7
2)	Gender of subjects	7
3)	Age of Subjects	7
4)	Racial and Ethnic Origin	7
5)	Inclusionary criteria	7
6)	Exclusionary criteria	7
7)	Subject withdrawal criteria	7
8)	Vulnerable subjects	7
III.	Methods and Procedures	8-13
1)	Methods and Procedures	8-11
2)	Schematic Diagram	12
3)	Data Analysis and Monitoring	13
4)	Data Storage and confidentiality	13
IV.	Risk and Benefit analysis	12-13
1)	Risk	12
2)	Protection against risk	12-13
3)	Potential benefits to subjects	13
V.	Investigators qualification and experience	13
VI.	Subject identification, recruitment and Consent/Accent	13-14
1)	Method of subject identification and recruitment	13
2)	Process of consent	13
3)	Subject capacity	13
4)	Subjects representative comprehension	13
5)	Debriefing procedures	13-14
6)	Consent forms	14
7)	Documentation of consent	14
8)	Cost to subjects	14
9)	Payment for participation	14
VII.	References Cited	15-17
VIII.	Appendix	18

Title of Research Project: Effectiveness of ASTYM treatment when added to traditional therapy for treatment of de Quervain's tenosynovitis

Principal Investigator: [name], MS, OTR/L

Co-Investigators: [name], OTR/L, CHT; [name], OTR/L, CHT, [name], OTR/L, CHT; [name], MS, MPH, OTR/L; [name], OTR/L, [name], OTR/L, CHT

IRB#-s 14-01059

I.Purpose of Study and Background

- **Purpose of study:**

To determine if the addition of Astym treatment to traditional therapy produces a more positive outcome than traditional therapy alone for the treatment of de Quervain's tenosynovitis.

- **Background:**

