In a case report by Baker and Wilson²³ examining Astym in the treatment of a bilateral carpal tunnel syndrome (CTS) patient, they found that Astym was shown to be an effective treatment approach for resolving the patient's symptoms. An article by Ettema et al²⁷ reported on the physiological changes that occur in the subsynovial layer of tissue during carpal tunnel. An electron microscope found fibrotic changes as a result of a shearing injury. The anatomy of the flexor tendons are similar to that of the tendons involved in de Quervain's. If Astym has been shown to be an effective treatment approach for

CTS, then it is reasonable to hypothesize that Astym would be an effective treatment for de Quervain's tenosynovitis. But does the Astym treatment along with stretching and exercise work better than the gold standard of care of splinting and exercise alone.

- **Study design:**

The research question for this study is:

Does adding an Astym treatment protocol to existing standard of care treatment of de Quervain's tenosynovitis increase outcomes of individuals with this condition?

The Alternative Hypothesis for this study is:

Participants receiving the Astym treatment protocol will have greater improvements in pain reduction and function as compared to those subjects in the control group receiving the standard of care therapy treatment

This is a randomized controlled study using repeated measure design with 2 groups:

- A. Control group who will receive standard of care rehabilitation intervention for the treatment of de Quervain's tenosynovitis.
- B. Experimental group will receive standard of care rehabilitation interventions plus Astym treatment protocol.

Three outcomes measures will be used for the study:

1. **Numeric Rating Scale for Pain**- This scale is a single point scale from 0-10. The participant picks one number to represent their pain, where 0 represents no pain and 10 represents worst pain imaginable.
2. **Quick Dash**-This is an 11 item questionnaire in which participants self-score themselves using a 1-5 point scale. One represents no difficulty in performing task whereas 5 represents unable to perform task.
3. **Sequential Occupational Dexterity Assessment**-This is a test to measure dexterity and bimanual abilities in activities of daily living. It includes 12 tasks with participants being scored on their ability, difficulty and pain during the task.

II. Characteristics of research population

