- **Number of subjects:** N=32 (16 in each group)
- **Gender of subjects:** Both male and female participants will be included in the study. Demographic data will be included in the analysis of results.
- **Age of subjects:** 18-65yrs old
- **Racial and ethnic origin:** There will be no racial or ethnic restrictions to this study. Data on racial/ethnic origin will not be gathered by the researchers. It is assumed based on current client population that the sample will be diverse.
- **Inclusion criteria:**
 - i. Positive Finkelstein's test: The client will report pain over the first compartment of the extensor retinaculum when the thumb is tucked in the hand and deviated ulnarily.
 - ii. Persistent symptoms for >3 wks which have not resolved after an additional 3 weeks of splinting
 - iii. A diagnosis by a physician of "de Quervain's", "fist compartment tenosynovitis", or "radial styloid tenosynovitis"
 - iv. Patients must agree and comply to a predetermined splinting regimen
- **Exclusion criteria:**
 - i. History of cortical steroid injection to affected wrist and/or thumb
 - ii. Comorbidity such as osteoarthritis, rheumatoid arthritis, auto-immune disease or inflammatory conditions.
 - iii. Clotting deficits
 - iv. Positive Cozen's sign which would indicate intersection syndrome³⁸
 - v. Post-partum mothers <6 months and pregnant women¹⁰⁻¹¹
 - vi. Cleared c-spine via Spurling's Test³⁴⁻³⁵ performed by combining cervical extension, side-bending, and axial compression to the cervical spine.
- **Vulnerable subjects:**
No vulnerable subjects will be included in this study

III. Methods and Procedures:

- **Methods and procedures:**
 - i. Randomized selection of 2 groups both seen for one evaluation and 12 therapy sessions scheduled 2x/week for 6 weeks (total of 12 sessions) for either traditional therapy including splinting and exercises or traditional therapy with Astym protocol. At least 2 days in between therapy sessions to allow sufficient healing.
 - ii. Randomization using computer-generated random numbers. The 3 Outcome measurements will be taken during evaluation and re-evaluation will be collected by two designated hand therapists other than the treating therapist. The data collectors will be blinded.

- iii. Data collection are taken at baseline, and after 12 sessions of therapy at discharge. . Quick DASH and VAS scale scores and questionnaire regarding patient compliance will be completed by phone interview at 3 month follow up.

Research design:

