Patients with the diagnosis of de Quervain's from referring physician will be provided with a pre-fabricated Ossur thumb spica splint for use as indicated in splinting program^{13,15-17}, instructed on a home exercise program as part of standard of care along with being educated about the research study. If interested, they will be consented, and scheduled for a follow-up visit 3 weeks later. If not interested, they will be scheduled for a 3 week follow-up session and treated if needed. Upon their return, the patients will be screened by the researcher OT for inclusion and exclusion criteria. If subject meets the criteria, they will be randomized into either (1) control or (2) Astym group and then evaluated by a blinded Certified Hand Therapist or hand therapist. Fine motor coordination will be tested by using the Sequential Occupational Dexterity Assessment (SODA)³⁹. Pain and functional loss will be measured via the Visual Analog Scale (VAS)⁴⁰ and Quick Dash⁴¹⁻⁴⁵. They are then seen for formal therapy 2/x for 6 weeks for a total of 12 therapy session. If the subject does not meet criteria or decide not to participate in

the study, they are deemed a screen failure, dismissed from study, and will continue with treatment if needed.

The subjects will be seen twice a week for 6 weeks for 30 minute sessions by a separate treating therapist from the evaluating therapist. The patient will start at phase I; however, will not progress to the next phase of treatment if symptoms and pain are provoked.. When he/she tolerates exercises without pain or exacerbation of symptoms, the patient is progressed to Phase II and then phase III .Prior to discharge, if the subject has not achieved phase III, the therapist will incorporate Phase III exercises, for strengthening and functional movements of the hand, forearm, elbow and shoulder to be completed at home. . All subjects, either in control or Astym group, will receive only 12 sessions of therapy regardless if they progress through the all 3 phases. Astym group will receive traditional therapy with Astym every session, while the control group will only receive traditional therapy. See protocol below.

Control group: Traditional therapy for de Quervain's Tenosynovitis^{17-19, 21-22, 30-33:}

Phase I: Reduction of splint use andstrengthening initiated once patient can perform pain free AROM (monitor symptoms to not exacerbate condition)

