 - UD of wrist with thumb tucked under fingers and wrist in neutral
 - Wrist flexion with elbow extended forearm pronated
 - Wrist extension with elbow extended forearm supinated
- Adding multi joint strengthening exercises to match job demands using dumbbells

Patient discharged to home exercise program after 12 sessions of therapy with review of ergonomics, stretches, and exercises at last session. **Astym group: Traditional therapy WITH Astym protocol for De Quervain's Tenosynovitis¹⁷:**

Phase II: Reduction of splint use and strengthening once patient can perform AROM pain free (monitor symptoms to not exacerbate condition)

- Goals include: teaching self-management techniques for long-term control, ergonomics education, regaining flexibility and tolerance to light functional tasks without pain, initiation of splint wean off program
- Moist heat pack for 10 minutes²⁸ at beginning of treatment
- **Astym treatment to affected extremity per de Quervain's protocol, including de Quervain's strokes (See Appendix I)**
- Stretching 4x/day for 30-45 seconds:
 - UD of wrist with thumb tucked under fingers and wrist in neutral
 - Wrist flexion with elbow extended forearm pronated
 - Wrist extension with elbow extended forearm supinated
- Isometric grip/pinch strengthening
 - Submaximal contractions to avoid increased microtrauma to musculotendinous unit
 - Strengthening started at 1 set of 5 reps, 2 seconds per rep working up to 6 seconds (as pain allows) 3x/day

Phase II: Progress to strengthening of wrist and hand with emphasis on eccentric loading

- Goals include: increasing tolerance to heavier demands of tasks without exacerbation of symptoms, return to normalcy of function without use of splint
- Moist heat pack for 10 minutes²⁸ at beginning of treatment
- **Continue Astym to affected extremity per de Quervain's protocol, including de Quervain's strokes**
- Advance patient once they can perform AROM, passive stretching of wrist, thumb and composite wrist/thumb, and isometrics pain free
- Using light theraband, 2 second count concentric motion followed by 4 second count eccentric motion for wrist strengthening in flexion, extension, radial and ulnar deviation with elbow flexed at 30-45* and forearm supported
- Gentle grip, chuck pinch, lateral pinch and thumb opposition strengthening into soft- medium putty starting at 15 repetitions building to 30 repetitions each without exacerbation of symptoms

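### The end-of-treatment assessment is timed by a 12-session count, so a patient who stops early has no such assessment and no post-baseline SODA at all

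*Combined protocol and SAP*

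**What the plan says.** Section III, item i, plans "12 therapy sessions scheduled 2x/week for 6 weeks (total of 12 sessions". Item ii has all three outcomes (pain, QuickDASH, SODA) measured at evaluation and re-evaluation. Item iii fixes the times: "Data collection are taken at baseline, and after 12 sessions of therapy at discharge". It adds that pain and QuickDASH, with a compliance questionnaire, "will be completed by phone interview at 3 month follow up". SODA is not part of that call.

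The control-group text ends: "Patient discharged to home exercise program after 12 sessions of therapy". The Astym-group text says the same, and a closing sentence counts the phone call from three months after discharge from the centre. The Research design text treats 12 sessions as applying to everyone.

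Section IV, Protection against risks, encourages patients to tell the therapist to stop if they have the listed side effects or no longer wish to be in the study. No assessment is attached to either choice. The table of contents lists "Subject withdrawal criteria" under section II, but the readable body has no such section.

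**The concern.** The trigger for the main post-treatment measurement is attendance, not time since randomisation. Attendance happens after randomisation and may depend on treatment and on how the patient is doing. The plan foresees early stopping but gives no assessment for those who stop.

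With 16 patients per arm, each missing patient is 1/16, or about 6%, of an arm, and no dropout allowance is stated. Loss unrelated to outcome costs only precision. Loss related to outcome, at different rates or for different reasons in the two arms, removes the balance that randomisation provided. Scores that were never collected cannot be restored in the analysis.

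**Working it through.** **1. Who has which measurement, following the text literally.**

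| Patient | Baseline | End of treatment | 3-month call |
|---|---|---|---|
| Completes 12 sessions | pain, QuickDASH, SODA | pain, QuickDASH, SODA | pain, QuickDASH |
| Stops sessions early | pain, QuickDASH, SODA | none provided for | pain, QuickDASH possible; start date unclear |

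Only SODA has no other planned post-baseline measurement.

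**2. The plan's own power figure.** The power paragraph gives 80% for the between factor with N = 32 and Cohen's f = 0.398. For m measures with correlation ρ, the noncentrality is λ = f²·N·m / (1 + (m − 1)ρ), with 1 and N − 2 degrees of freedom. Neither m nor ρ is stated. With m = 2, 80% needs ρ of about 0.21: λ = 0.158 × 32 × 2 / 1.21 = 8.4. With m = 3 it needs ρ of about 0.41. The figure is therefore attainable but can be neither confirmed nor refuted. On that calibration, with losses split evenly, 28 patients left give 74.1% and 24 left give 66.9%.

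**3. Precision if loss is unrelated to outcome.** The standard error ratio is √((1/(16 − k) + 1/16) / (2/16)). For k = 1 lost from one arm it is 1.017; for k = 4 it is 1.080. Bias is 0.

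**4. Bias if loss is related to outcome.** All inputs here except 16 per arm and alpha 0.05 are assumptions. There is no true effect. Baseline and discharge scores are normal with equal SD and correlation 0.2 or 0.5. The k patients lowest on a variable that has correlation r with improvement stop and are left out. The test is a two-sample t-test on change, which equals the group-by-time test when there are two time points.

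The expected bias, in SD of change, is r × (sum of the k largest expected order statistics of 16 standard normals) / (16 − k). Those values are 1.766, 1.285, 0.990 and 0.763.
- k = 1, r = 0.2: 0.2 × 1.766/15 = 0.02
- k = 4, r = 0.5: 0.5 × 4.804/12 = 0.20
- 3 lost per arm, worst improvers in Astym and best in control, r = 0.5: 2 × 0.5 × 4.041/13 = 0.31

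Simulation (100,000 trials per case, error about 0.1 percentage point) agrees and gives the chance of a significant result favouring Astym, nominally 2.5%:

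| Assumed stopping | Group-by-time bias (SD) | Favouring Astym |
|---|---|---|
| Worst improvers, Astym only, 1 to 4, r 0.2 to 0.5 | +0.02 to +0.20 | 2.9% to 7.7% |
| Worst final scores, Astym only, same range | +0.01 to +0.13 | 2.7% to 5.1% |
| Worst improvers, control only, same range | −0.02 to −0.20 | 2.1% down to 0.7% |
| Best improvers (recovered), Astym only, 4, r = 0.5 | −0.20 | 0.7% |
| 3 per arm, same reason | 0 | 2.5% to 2.9% |
| 3 per arm, opposite reasons, r = 0.5 | +0.31 | 13% |
| Unrelated to outcome | 0 | 2.4% to 2.6% |

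With 1 or 2 Astym stoppers and r = 0.2, the chance is at most 3.4%.

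**5. The between-factor test, which the plan powers.** If stopping tracks improvement and the two SDs are equal, its bias is 0.00 SD (2.4% to 2.6%). That depends on equal SDs. With a discharge SD of 0.7 or 1.5 times baseline (k = 4, r = 0.5), the bias is about −0.07 to −0.08 SD or +0.08 to +0.09 SD. If stopping tracks the final score, equal SDs give 0.02 to 0.17 SD and 2.8% to 6.5%.

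**The case against.** **The phone call remains.** A reader might infer that an early stopper has no post-treatment data of any kind. The documents do not support that: item iii schedules the call with no condition on sessions attended, and discharge from the centre can mean simply leaving the clinic. This stands, and limits the point to the end-of-treatment assessment and SODA.

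**Nothing forbids a week-6 assessment.** True. The text provides for none, and a rule may sit in the withdrawal section, the schematic diagram or the consent form, which cannot be read here. This lowers confidence but does not fill the gap in item iii.

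**Bias towards Astym is not shown.** A reader might infer it because the listed side effects belong to Astym. The protocol calls them temporary, and a request to stop may concern one session only. Control patients also have reasons to leave: everyone enters with "Persistent symptoms for >3 wks which have not resolved after an additional 3 weeks of splinting", and in both arms a patient "will not progress to the next phase of treatment if symptoms and pain are provoked". Patients who recover may stop too, which reverses the sign. Equal loss is harmless only if the reasons are the same in both arms.

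**The simulated tests may not be the planned ones.** The plan's sphericity test matters only with three or more time points, and pain and QuickDASH have three. The two-time-point equivalence is certain only for SODA. The figures are illustrations, and no stated rule says how the planned analysis treats a missing score.

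**Some patients will leave altogether.** Re-timing the visit helps only those who stop sessions but remain available. This stands.

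**Conclusion.** The point holds as a gap in the schedule: item iii makes the end-of-treatment assessment depend on 12 sessions, and no readable text covers patients who do not reach that count. The group-by-time test bears most directly on the hypothesis that Astym patients "will have greater improvements in pain reduction and function", and it can be biased in either direction if stopping is related to outcome and its rate or reasons differ between arms.

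The size is not known. The illustrated range of 2.9% to 7.7% rests on Astym-only loss of the worst improvers, equal SDs, two time points and correlations of 0.2 to 0.5. The effect is small at the low end, and nil if loss is unrelated to outcome or matched in both number and reason. Confidence is medium. This is a cheap improvement to make, not evidence that the trial's result is or will be biased.

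**What to change.** In section III, item iii: assess pain, QuickDASH and SODA in every randomised patient at the end of the scheduled 6 weeks, whatever number of sessions was attended, with the same stated window in both arms (for example up to 2 weeks). If a patient will not attend, take pain and QuickDASH by phone within that window; SODA would then be missing. Time the phone call three months from that date.

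In section IV: separate stopping Astym or therapy sessions from leaving the study, with the right to do either unchanged.

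The cost is protocol wording, plus an already planned visit (or a phone call) and an already planned follow-up call for the patients who stop early. Patients on schedule are unaffected. The downsides are modest: some patients are assessed with fewer than 12 sessions or while still in treatment, a few scores come by phone, and the estimated effect may be slightly smaller. Patients who leave the study altogether are not recovered.

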- Thumb abduction and extension with yellow power web or light resistance rubber bands 3 sets of 10 reps
- Continue stretching 4x/day for 30-45 seconds, with stretching prior to and after exercises:
 - UD of wrist with thumb tucked under fingers and wrist in neutral
 - Wrist flexion with elbow extended forearm pronated
 - Wrist extension with elbow extended forearm supinated

Phase III: Continue therapy, incorporate strengthening and functional movements for forearm, elbow and shoulder and prepare patient for discharge to home exercise program

- Goals include: Pain free functional use of affected extremity during all tasks without use of splint
- Replace moist heat pack with Upper Body Ergometer for 10 min
- **Continue Astym to affected extremity per de Quervain's protocol, including de Quervain's strokes for a max of 12 sessions**
- Continue stretching 4x/day for 30-45 seconds, with stretching prior to and after exercises:
 - UD of wrist with thumb tucked under fingers and wrist in neutral
 - Wrist flexion with elbow extended forearm pronated
 - Wrist extension with elbow extended forearm supinated
- Adding multi joint strengthening exercises to match job demands using dumbbells
- Patient discharged to HEP after 12 sessions of therapy with review of ergonomics, stretches, and exercises at last session.

Three months after discharge from CMC, Quick DASH and VAS scale scores and questionnaire regarding patient compliance will be completed by phone interview.

Data Analysis and Monitoring

Descriptive statistics will be used along with inferential statistics. The alternative hypothesis will be addressed using a mixed design analysis of variance to test for differences between-groups and within-groups. In addition we will also analyze the interaction effect between study group and time. All analyses will have an alpha of 0.05. Malchy's test for sphericity will be performed along with a Bonferroni comparison. If Malchy's test for sphericity is significant then a Greenhouse-Geisser or Huynh-Feldt correction will be used. In addition a repeated measure MANOVA may be used to test the dependent variables in a multivariate method if in fact the dependent variables demonstrate a relationship of linearity.

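### Patients are randomised before the self-rated baseline is taken, nothing delays disclosure of the arm, and the recruitment section gives a different order of consent and evaluation

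*Combined protocol and SAP*

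**What the plan says.** **Order of events.** Under Research design in section III, patients receive a splint and home exercises and hear about the study. Those interested consent and return three weeks later for the eligibility screen. Those eligible then follow this order: "they will be randomized into either (1) control or (2) Astym group and then evaluated by a blinded Certified Hand Therapist or hand therapist". SODA, pain and Quick DASH are described next, and therapy with a separate treating therapist comes after them.

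**That evaluation is the outcome baseline.** Methods and procedures, item i, has both groups "both seen for one evaluation and 12 therapy sessions". Item ii adds: "The 3 Outcome measurements will be taken during evaluation and re-evaluation". Item iii adds: "Data collection are taken at baseline, and after 12 sessions of therapy at discharge". Pain and Quick DASH are collected again by phone at three months.

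**Blinding.** Item ii says "The data collectors will be blinded", and the evaluating therapist is also called blinded. The text makes no statement about patients or about when the arm is disclosed.

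**Who rates.** In section I, Study design, for pain: "The participant picks one number to represent their pain". For Quick DASH: "participants self-score themselves using a 1-5 point scale". The text does not say who rates the difficulty and pain parts of SODA.

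**Analysis.** Data Analysis and Monitoring specifies a mixed ANOVA: "In addition we will also analyze the interaction effect between study group and time". The power statement concerns the between-group factor.

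**Second account of the sequence.** Section VI, on identification and recruitment, gives out the consent form after a first evaluation by a blinded therapist who does not treat the patient. Process of Consent places it after the clinician has judged the patient suitable.

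**The concern.** A blinded evaluator protects scores that the evaluator assigns. It does not protect a score chosen by a patient who already knows the arm. A patient told of assignment to the added treatment, or to usual therapy alone, may rate pain or function differently at that moment. Such a shift would be a consequence of allocation and not a chance imbalance, yet the analysis would treat it as the starting point.

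The hypothesis in section I is about greater improvement, so the group-by-time interaction is the contrast that addresses it. A difference present at baseline only goes into that contrast in full, and its direction cannot be known in advance. With 16 patients per arm, a baseline comparison would rarely reveal it.

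The two accounts of the sequence add a separate difficulty: a reader cannot tell which evaluation is the baseline, or whether it comes before or after consent and randomisation.

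**Working it through.** **1. The sequences side by side**

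| Step | Section III, Research design | Section VI |
|---|---|---|
| 1 | Consent at first contact | Evaluation by a blinded, non-treating therapist; judgement of suitability |
| 2 | Three weeks of splinting, then eligibility screen | Consent form and study information |
| 3 | Randomisation | Not placed |
| 4 | Blinded evaluation with all three outcomes | Not placed |

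Item i counts one evaluation per patient. If section VI describes that evaluation, it comes before consent, which contradicts section III. If it is a separate intake step, section III does not mention it. Inclusion criterion ii needs three further weeks of splinting, so full eligibility cannot be judged at section III's consent visit. If suitability in section VI means eligibility, the timing of consent conflicts as well.

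**2. The plan's own figure**

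The plan states 80% power for the between factor with N = 32 and f = 0.398. With m visits, λ = N f² m / (1 + (m−1)ρ) on 1 and 30 df. This gives 80.3% for m = 2, ρ = 0.2 and for m = 3, ρ = 0.4. The plan states neither m nor ρ, so 80% is attainable but cannot be confirmed. The present point does not depend on it.

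**3. Effect of a baseline shift**

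From the plan: N = 32, 16 per arm, alpha 0.05; k = 3 visits for pain and Quick DASH, k = 2 for SODA. Assumed, because the documents give no values: SD 1, compound symmetry, ρ = 0.4, 0.5 or 0.6, no true effect, and a shift s between arms at baseline only.

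- Interaction: df k−1 and 30(k−1); λ = (N/4) s² ((k−1)/k) / (1−ρ).
- Between factor: df 1 and 30; λ = (N/4)(s/k)² / ((1+(k−1)ρ)/k).
- Baseline t-test: df 30; λ = (N/4) s².

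Example with s = 0.5, k = 3, ρ = 0.5:

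- Interaction: λ = 8 × 0.25 × (2/3) / 0.5 = 2.667, rejection rate 27.7%.
- Between factor: λ = 8 × (0.5/3)² / (2/3) = 0.333, rejection rate 8.65%.
- Baseline t-test: λ = 8 × 0.25 = 2.0, rejection rate 27.8%.

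Rejection rates at nominal 5%, over ρ = 0.4 to 0.6:

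| Test | s = 0.1 | s = 0.25 | s = 0.5 |
|---|---|---|---|
| Interaction, 3 visits | 5.6–6.0% | 9.2–11.4% | 24–34% |
| Interaction, 2 visits | 5.7–6.1% | 9.6–11.9% | 24–33% |
| Between factor, 3 visits | 5.1–5.2% | 5.8–6.0% | 8.3–9.1% |
| Between factor, 2 visits | 5.3% | 6.7–6.9% | 11.9–13.0% |
| Baseline t-test flags the shift | 5.9% | 10.5% | 28% |

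The two-visit rows apply to SODA only so far as its components are rated by the patient.

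Simulation with 20,000 trials per setting, at s = 0.5 and ρ = 0.4 and 0.6, agrees: interaction with three visits 23.5% and 33.7%; between factor 9.0% and 8.2% with three visits, 12.9% and 12.2% with two. With no shift, all rates lay between 4.7% and 5.3%.

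**4. If part of the shift persists**

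If half of s remains at each later visit, the interaction sees a net shift of s/2. With three visits the rates become 5.2%, 6.0–6.5% and 9.2–11.5%. If the shift is equal at every visit, the interaction test stays at 5%.

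**The case against.** The strongest reply is that the bias needs an event the text does not describe. The evaluation follows randomisation directly, is done by a blinded therapist, and comes before therapy begins. The arms differ only in what happens in the therapy sessions, so no described step requires the patient to know the arm earlier. If patients learn it at the first session, there is no bias by this route. The table of contents also lists a schematic diagram, and the consent forms are held separately. Neither was available here, and either might state the timing.

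Second, the larger figures assume that the shift disappears after baseline, although a patient who knows the arm at baseline still knows it later. Step 4 shows how much partial persistence reduces them. The between factor, which is the test the plan powers, is less affected throughout.

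Third, if section VI's evaluation is the outcome baseline, then baseline precedes randomisation and the bias route disappears under that account. If it is an intake, it does not contradict the randomise-then-evaluate order.

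All three stand as limits on weight. They do not remove the explicit order in section III, the lack of any visible statement that withholds the arm from patients, or the need to reconcile two accounts that differ on either reading.

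**Conclusion.** The concern holds and should be fixed, with medium confidence. Two parts are matters of text: section III randomises before the outcome baseline, and section VI orders consent and evaluation differently. The bias itself is possible and not demonstrated. It needs patients to know their arm before completing the baseline forms, and it needs their ratings to shift more at baseline than later.

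Given those conditions and the assumed values, the interaction test ranges from negligible inflation (about one percentage point or less at 0.1 SD) to 24–34% at 0.5 SD with no persistence. The upper end combines the largest assumed shift with its complete disappearance after baseline, so it is not a forecast. A baseline comparison offers little protection, since it would miss even a 0.5 SD shift in about 72% of trials (100% − 28%).

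Unblinded self-rating at discharge and at three months is a separate matter, which this point does not address.

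**What to change.** In Research design, place the blinded baseline evaluation (pain, Quick DASH, SODA) after the eligibility screen and before randomisation. State that the allocation is generated or revealed only once the baseline forms are complete. This closes the route whatever the present disclosure practice is.

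Rewrite section VI to match, so that the protocol gives one order: consent, eligibility, baseline, randomisation. Say whether the evaluation described in section VI is the outcome baseline or a separate intake.

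The cost is a short amendment that reorders two existing steps. It needs no extra staff, procedures or patients, and the sample size does not change. The text does not say whether screening, randomisation and evaluation fall on one visit, so any effect on scheduling cannot be judged from it.
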